

Item 4 Purpose and rationale Insert purpose, objectives and research questions/hypotheses here. If you cut and paste from another document, make sure the excerpted material answers the question
	
We propose a randomized, double-blind, sham-controlled, 20 consecutive day trial of adjunct TMS to the right DLPFC in active duty service members and veterans with PTSD receiving an integrated and evidence-based treatment (i.e. TAU) for PTSD incorporating both adequate pharmacological approaches and Cognitive behavioral therapy (CBT) at Laurel Ridge Treatment Center (LRTC). In addition to TAU, consented patients will be randomized to receive irTMS in one of two treatment arms: Arm 1 delivers active irTMS to the right DLPFC. Arm 2 delivers sham TMS (inactive coil) to the right DLPFC. To ensure equivalent placebo effects across arms, sham TMS delivers the exact sound produced during active irTMS, therefore patients are unable to discriminate between sham and active TMS. Moreover, clinicians providing TAU at LRTC and researchers conducting clinical outcomes assessments will be blinded to each participants' treatment arm. Resting-state fMRIs (rs-fMRIs) will be used both for treatment planning (baseline imaging), which guides the individualized positioning of the TMS coil, and to characterize TMS-induced network connectivity (imaging treatment week 3). Self-report scales will be done weekly at LRTC. A 1-month post-treatment clinical follow-up will be conducted in person or over the phone to evaluate maintenance of clinical outcomes. Considering that depressive symptomatology, often meeting diagnostic criteria Major Depressive Disorder (MDD), is commonly observed in patients with PTSD, patients with comorbid PTSD and MDD won't be excluded from the study and we will also assess depressive symptoms throughout treatment at the same time intervals—i.e., baseline, weekly, and 1 month post-treatment.
 
Aim 1. Test whether compared with TAU plus sham irTMS, TAU plus adjunct active irTMS is associated with greater clinical improvement that differs in specificity to PTSD or depressive symptomatology according to the targeting of right DLPFC .
 
 Hypothesis 1. TAU plus adjunct active irTMS to the right DLPFC will be superior to TAU plus sham irTMS in relieving PTSD symptoms. 
Aim 2. Test for irTMS-induced changes in network functionality (plasticity) using rs-fMRI.
 
 Hypothesis 2a. Intrinsic connectivity will be attenuated by active irTMS in networks connected to the respective treatment sites, as tested by correlation with the number of sessions received at the time of scanning and by pre-treatment-to-post-treatment contrast. Hypothesis 2b. Treatment-induced decreases in connectivity will correlate with symptom improvement within and across treatment arms.

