
Patients diagnosed by the LRTC with PTSD, receiving evidenced based combined pharmacological and psychotherapy (either PE or CPT)
	
 1) Male or female English-speaking active duty or recently retired veteran patients who have deployed post 9/11 receiving treatment at LRTC between the ages of 18-65 years; 2) Patients must have a diagnosis of PTSD confirmed by the Clinician-Administered PTSD Scale (CAPS-5) at screening, 3) Subjects must have a minimum PTSD Symptom Checklist for DSM-V (PCL-5) symptom severity rating of 25. 	
 1) Subjects with a diagnostic history of bipolar disorder, schizophrenia or schizoaffective disorder as documented in the medical record. 2) Substance use disorder during the 12 months prior to screening; except that Mild - Moderate, but not Severe, Alcohol Use Disorder (using DSM-5 criteria) will be allowed as determined by LRTC medical provider review. 3) Any history or signs of serious medical or neurological illness including seizure disorders. Except for seizures, a subject with a clinical abnormality may be included only if the study clinician considers the illness will not introduce additional risk and will not interfere with the study procedures. This will be determined during the screening phase via self-report and/or medical history review. 4) History of traumatic brain injury (TBI) with loss of consciousness for 20 minutes or more as determined by the History of Head Injuries questionnaire. 5) Females will be excluded if they are pregnant (i.e. positive pregnancy test identified after their LRTC intake). 6) Any history or signs of metal objects deemed unsafe for MRI or that may adversely affect image quality of the brain region (e.g. surgical clips, cardiac pacemakers, metal implants, etc.) in the body at the time of screening as indicated by self-report. MRI can have risks for persons with foreign bodies implanted in their body.

Item 6
Research Plan / Description of the Research Methods a. *Provide a comprehensive narrative describing the research methods.*
Provide the plan for data analysis (include as applicable the sample size calculation).

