Step-by-Step Methods: We propose to test 100 patients (i.e. 50 per arm) who meet criteria for PTSD as determined by the Clinician Administered PTSD Scale (CAPS-5) and the outlined study inclusion criteria. We anticipate consenting and screening approximately 200 male and female subjects, in order to meet the target enrollment goals. To account for subject dropouts and retain a sample of 100 subjects completing the double-blind treatment phase (50 per treatment group), 132 eligible subjects (66 in each group) meeting the study inclusion criteria will be randomized for the study. See also Table of Study Procedures below.

Recruitment

Patients will be recruited at LRTC from institution's PTSD inpatient program by the study staff supervised by the On-site Investigator's team. Upon admission to the LRTC, patients will be informed about this treatment trial by either their staff psychiatrist or a member of the LRTC's research team. Each patient will be given an information sheet describing the study. If interested in participating, each patient will be shown a video describing the treatment trial and each of the tools/treatments used throughout the study (i.e. MRI and TMS).

Pre-Screening and LRTC Intake

Under an IRB approved HIPAA Waiver of Authorization, Waiver of Informed Consent, and Waiver of Documentation of Informed Consent, study personnel will conduct a brief pre-screening intake interview where the basic study inclusion and exclusion criteria will be reviewed to help the individual determine if he or she meets the study criteria or has obvious exclusions from the study protocol. This information will be maintained as a secure file with the following information: name, phone number, name of study, referral date, referral source, potential eligibility status, reason if not eligible, and verbal permission to contact the caller in the future for other studies. Subjects who agree to study participation will sign a consent document before any further screening will take place. Any individually identifiable information and Protected Health Information (PHI) collected on individuals who do not consent to participation will not become part of the research data. If subjects agree to participate in the research, the identifiable data collected will become part of the subjects' research records and will be stored according to the research confidentiality plan.

Consent Process

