3. *Clinician-Administered PTSD Scale for DSM-5 (CAPS-5)* is a structured diagnostic interview and gold standard for assessing PTSD. It has excellent psychometric properties and diagnostic efficiency (Weathers, Keane, & Davidson, 2001). The scale also assesses social and occupational functioning, dissociation, and the validity of symptom reports. The CAPS was revised to accommodate the changes made in DSM-5, to reduce administration time, and to facilitate learning administration and scoring procedures. The CAPS for DSM-5 (CAPS-5; Weathers et al., 2013) now uses only a single 5-point ordinal rating scale to measure symptom severity. Symptom severity ratings combine information about symptom frequency and intensity obtained by the interviewer. CAPS-5 scores range from 0 to 80 with higher scores indicating greater PTSD symptom severity. At the same time, the CAPS-5 was revised with an eye toward maintaining backward compatibility with the DSM-IV version of the instrument. Because the measure is new, psychometrics and diagnostic cutoffs are still being evaluated. The CAPS-5 will be administered by certified independent evaluators (IE) blind to treatment status at the beginning and end of the intervention for all participants. Studies conducted near San Antonio and Fort Hood will be able to utilize IEs who receive training and ongoing support by the CAP Assessment Core. Remote studies will need to supply IEs for the various administrations of the CAPS-5. These staff will adhere to the Assessment Core's standardized procedures.
4. *PTSD Checklist for DSM-5 (PCL-5; Weathers, Litz, Keane, Palmieri, Marx, & Schnurr, 2013)* is similar in form to the PTSD Checklist (PCL) based on the DSM-IV (Weathers, Litz, Herman, Huska, & Keane, 1993). The PCL has excellent psychometric characteristics for screening and as a secondary indicator of PTSD symptom severity (see McDonald & Calhoun, 2010). The PCL-5 is a 20-item self-report measure, selected for its dimensional sensitivity, with higher scores reflecting greater PTSD severity. Scoring is based on how much the patient has been bothered by the symptoms in the past month on a scale from "0 = not at all" to "4 = extremely."

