Clinical Outcomes Data Analysis plan. All pre-treatment and post-treatment MRIs will be acquired and analyzed at the RII, however, all of the statistical analysis of the symptom scores for this project will be done upon completion of recruitment and termination group blinding. The primary efficacy outcome measure will be the PTSD Checklist (PCL-5) for symptoms assessed pre-treatment, weekly during treatment, post-treatment, and 1-month following the completion of treatment and the Clinician-Administered PTSD Scale for DSM-5 (CAPS-5) for the diagnosis of PTSD assessed pre-treatment and 1-month following the completion of treatment. The primary analysis will use mixed effects regression models. Secondary analysis will focus on changes in PTSD symptoms clusters, effects of the intervention in mood symptoms, functioning and cognitive outcomes. Types and rates of adverse events will be summarized and compared across the study groups. The durability of benefit and the clinical significance of PCL changes will be explored. Non-compliance to protocol as defined as missing two consecutive iTMS sessions or receiving less than 16 iTMS sessions during hospitalization at LRTC will be assessed for and evaluated in data analysis.

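### PCL-5 and CAPS-5 are both primary for one hypothesis, with no order, success rule, error control or deciding PCL-5 contrast, and the CAPS-5 variable is not settled

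*Combined protocol and SAP*

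**What the plan says.** Item 4 states one clinical hypothesis, Hypothesis 1: "TAU plus adjunct active irTMS to the right DLPFC will be superior to TAU plus sham irTMS in relieving" PTSD symptoms. It names no scale and no visit.

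Item 6, Clinical Outcomes Data Analysis plan, uses the singular but then lists two measures. First: "The primary efficacy outcome measure will be the PTSD Checklist (PCL-5) for symptoms assessed pre-treatment, weekly during treatment, post-treatment, and 1-month" after treatment. Second: "and the Clinician-Administered PTSD Scale for DSM-5 (CAPS-5) for the diagnosis of PTSD assessed pre-treatment and 1-month following the completion of treatment". On method it says only: "The primary analysis will use mixed effects regression models". No alpha, sidedness, contrast, ranking or multiplicity method appears there or anywhere else in the document.

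Three other places bear on CAPS-5. Item 5, inclusion criterion 2: "Patients must have a diagnosis of PTSD confirmed by the Clinician-Administered PTSD Scale (CAPS-5) at screening". Item 6, baseline measure 3: "CAPS-5 scores range from 0 to 80 with higher scores indicating greater PTSD symptom severity". The same measure description places the interview at the start and end of the intervention. The analysis plan instead says pre-treatment and 1 month, and the Table of Study Procedures marks baseline and the combined 1/3-month column.

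**The concern.** Suppose active wins on PCL-5 at the end of treatment and CAPS-5 at 1 month shows nothing. The plan cannot say whether that trial succeeded. If either outcome is enough, two chances are taken at one claim. If both are needed, the trial is harder to win than a single-outcome design of the same size. PCL-5 adds a further choice: weekly, post-treatment and 1-month values could give a group difference at one visit, an average over visits or a group-by-time test, and these need not agree.

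The CAPS-5 wording matters separately. If the variable is the diagnosis, every participant is positive at entry, so the pre-treatment value is constant and cannot inform a model. The information in the 0-80 score is also discarded.

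**Working it through.** **Inputs from the document.** The target is to "retain a sample of 100 subjects completing the double-blind treatment phase (50 per treatment group"), from "132 eligible subjects (66 in each group"). This sample size cannot be reproduced, because no alpha, power or effect size is given. The step from 100 to 132 implies dropout of 1 - 100/132 = 24.2%, which is not stated either.

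**Assumptions, not in the document.** Two-sided 0.05; 50 per arm analysed; an effect of 0.566 SD, chosen because it gives 80% power at that size; correlation 0.5-0.9 between the two test statistics; PCL-5 treated as one unadjusted comparison.

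**1. Either outcome suffices.** With both null hypotheses true and (Z1, Z2) bivariate normal with correlation r, the error is 1 - P(|Z1| < 1.96, |Z2| < 1.96). The part favouring active is 1 - P(Z1 < 1.96, Z2 < 1.96).

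- r = 0.5: 9.07%, of which 4.54% favours active
- r = 0.7: 8.35%, of which 4.17%
- r = 0.9: 7.04%, of which 3.52%
- r = 0: 9.75%, of which 4.94%

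One test gives 5% and 2.5%. At r 0.5-0.9 the false claim for active is therefore 4.54/2.5 = 1.8 down to 3.52/2.5 = 1.4 times as likely.

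**2. Both must succeed.** There is no inflation. For one severity outcome the noncentrality is 0.566 × √(50/2) = 2.83 on 98 degrees of freedom, giving power 0.800. With each outcome at 80%, the bivariate normal gives joint power 0.687 at r = 0.5 and 0.750 at r = 0.9.

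**3. CAPS-5 score against diagnosis.** Treat the diagnosis as one cut of a normal score. If a proportion p of sham patients still has the diagnosis, the active proportion is Φ(Φ⁻¹(p) - 0.566). Power from the pooled two-proportion approximation, 50 per arm:

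- p = 0.30, active 0.138: 50.1%
- p = 0.60, active 0.377: 60.8%
- p = 0.80, active 0.609: 55.6%

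Unadjusted severity has 80.0%. Adjusting severity for baseline divides the noncentrality by √(1 - ρ²), giving 83.6% at ρ = 0.3 and 89.9% at ρ = 0.5.

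**4. Cost of Hochberg.** Uncontrolled, the chance of winning at least one outcome is 0.80 + 0.80 - 0.687 = 0.913 at r = 0.5 and 1.60 - 0.750 = 0.850 at r = 0.9. Under Hochberg (both at 0.05, or one alone at 0.025) it is about 86% and 79-80%. The normal approximation, in which each outcome alone has 81%, raises these by up to about 1 point. The fall is thus from about 85-92% to about 79-87%.

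**The case against.** **Diagnosis may describe the instrument, not the variable.** The analysis plan itself speaks of analysing symptom scores, the second aim in the abstract relies on clinicians' ratings alongside self-report, and the measure description gives a severity score. This stands. A reader might infer that the trial is committed to a binary CAPS-5 endpoint; the documents do not settle that. The supportable statement is that the variable is undefined, and every diagnosis-power figure is conditional on the literal wording. Nor can one say that no diagnostic rule exists: the description calls cut-offs unsettled, but it also refers to standardised assessment procedures that are not in this document.

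**Hypothesis 1 may belong to PCL-5 alone.** It concerns symptoms, and PCL-5 is the measure assigned to symptoms. That is a plausible reading, but the plan still calls both measures primary and does not adopt it.

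**A mixed model can give one overall PCL-5 test.** It can, so what is missing is a named contrast, not necessarily a single visit. For the same reason, a reader should not add a separate penalty for free choice among PCL-5 visits; the text does not show that such a choice is intended.

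**The main time point is hinted at.** Item 4 says the 1-month visit evaluates maintenance, and the analysis plan makes durability exploratory. Both suggest end of treatment for PCL-5. Neither says so, but any fix must deal with them.

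**A doubling of error is too strong.** It needs zero correlation between two PTSD scales in the same patients.

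**The timing conflict is small.** The analysis plan and the Table of Study Procedures are compatible. The description that differs reads as general consortium text.

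**Conclusion.** The concern holds for the missing order, success rule, error control and PCL-5 contrast. This is read directly from the text and should be fixed before unblinding, because the trial's main conclusion depends on it. Its size depends on which rule is later applied: 7.0-9.1% false positives (9.8% if independent) under an either-wins rule, or no inflation and joint power of 69-75% instead of 80% if both must win. It would be wrong to say that the plan as written has inflated error, since it does not say which rule applies.

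The second part holds only conditionally. The CAPS-5 variable is unsettled. If the literal diagnosis wording is followed, illustrative power is 50-61% against 80% for severity, for sham retention of 30-80%; the 50% figure belongs to the 30% extreme. Alpha, effect size, correlations, retention and the single-cut model are all assumptions, and a repeated-measures PCL-5 model would change the joint figures.

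**What to change.** In the Clinical Outcomes Data Analysis plan:

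- Name one primary active-minus-sham contrast from the mixed model on one measure. Test the other measure next in a fixed sequence, each at 0.05. If both must stay primary, use Hochberg. The sponsor chooses the order and records it before unblinding.
- When choosing the PCL-5 contrast, address the statements that 1 month evaluates maintenance and that durability is exploratory, both of which suggest end of treatment. CAPS-5 is scheduled after baseline only at follow-up, so the two measures may need different time points.
- Analyse CAPS-5 as 0-80 total severity at 1 month, adjusted for baseline severity. Make loss of diagnosis a secondary outcome with its scoring rule stated, compared between arms at follow-up only.
- As a minor point, reconcile the CAPS-5 timing in the measure description with the analysis plan and the Table of Study Procedures.

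Keeping CAPS-5 at 1 month needs wording only. If the end-of-intervention timing were kept instead, an assessment would have to be added to the schedule. The statistical price of a fixed sequence is that the second outcome can be claimed only if the first succeeds, while the first keeps its full single-test power. The price of Hochberg is that an outcome winning alone must reach 0.025, with the loss in power shown in step 4.

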3. Clinician-Administered PTSD Scale for DSM-5 (CAPS-5)		X						X
4. PTSD Checklist for DSM-5 (PCL-5)		X		X	X	X		X
5. Life Events Checklist - 5 (LEC-5)		X						X
6. Deployment Risk and Resiliency Inventory-2 (DRRI-2) Combat and Postbattle Experiences Subscales		X						
7. Patient Health Questionnaire-9 (PHQ-9)		X		X	X	X		X
8. 'Structured Interview Guide for the Montgomery-Åsberg Depression Rating Scale (SIGMA).pdf'		X				X		X
9. Generalized Anxiety Disorder Screen (GAD-7)		X		X	X	X		X
10. Alcohol Use Disorders Identification Test (AUDIT) self-report version		X						X
11. Quick Drinking Screen (QDS) self-report version		X						X
12. Fagerstrom Test for Nicotine Dependence		X				X		X

13. Fagerstrom Test for Nicotine Dependence – Smokeless Tobacco		X				X		X
14. Insomnia Severity Index (ISI)		X				X		X
15. Snoring, Tired, Observed, Blood Pressure (STOP) Sleep Apnea Screen		X						
16. Patient Reported Outcomes Measurement Information System (PROMIS) Sleep Disturbance and Sleep-Related Impairment short forms		X				X		X
17. Depressive Symptoms Index – Suicidality Subscale		X				X		X
18. Self-Injurious Thoughts and Behaviors Interview short form		X				X		X
19. Veterans RAND 12-Item Short Form Health Survey (VR-12)		X						X
20. Brief Inventory of Psychosocial Functioning (B-IPF)		X						X
21. Health Questionnaire		X				X		X
22. Clinical Global Impressions (CGI)		X				X		X
Adverse Events Monitoring			X	X-X	X-X	X-X		X
Concomitant Medications/Treatment	X-X	X-X		X-X	X-X	X-X		X
Structural MRI			X					
Intrinsic Connectivity by Blood-Oxygen-Level-Dependent Functional MRI			X				X	
Motor threshold assessment			X				X	
irTMS Treatment (20 consecutive days)				X-X	X-X	X-X		
Participant Blind Form							X	
Independent Evaluator Blind Form								X

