Discontinuation of Subjects. Subjects may be discontinued from study treatment and assessments at any time. Specific reasons for discontinuing a subject from this study are: 1) Voluntary discontinuation by the subject, who is at any time free to discontinue his/her participation in the study without prejudice to further treatment; 2) Clinical deterioration: The following are objective criteria for clinical deterioration, (a) a 25% increase in the PCL-5 at any time during the study, (b) Patients with a CGI-I score ≥ 6 at any post-baseline visit, and (c) the onset of active suicidality as assessed by the study clinicians requiring treatment outside of the study protocol; 3) Evidence of intolerable adverse reaction, or unable to tolerate iTMS or MRI; 4) Safety reasons as judged by the investigator.

Potential Benefits.

- The potential benefit to participants is the potential for PTSD and/or depressive symptom relief.

Adverse Events, Unanticipated Problems, and Deviations.

Adverse Events will be assessed and monitored according to the established STRONG STAR and CAP SOPs and the IRB of record's policies and procedures. Reporting Adverse Events, Unanticipated Problems Involving Risks to Subjects or Others (UPIRSOs), and Deviations to the Office of the IRB. All adverse events, unanticipated problems involving risk to subjects or others, and deviations will be reported to the Institutional Review Board (IRB) in accordance with current IRB policy. UPIRSOs and recurrent non-compliance with study procedures will be reported promptly to the IRB. All adverse events that do not meet the UPIRSO criteria and deviations that are not non-compliance will be summarized at Continuing Review per the IRB of record's policy.

Research Monitor.

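### If 1-month CAPS-5 is lost after a PCL-5 rise and that loss differs by arm, a CAPS-5-only model is biased; the PCL-5 readings already scheduled could largely correct it

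*Combined protocol and SAP*

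**What the plan says.** - **Outcomes and model.** The Clinical Outcomes Data Analysis plan (Item 6) names as primary the "PTSD Checklist (PCL-5) for symptoms assessed pre-treatment, weekly during treatment, post-treatment, and 1-month following the completion of treatment", together with CAPS-5 "for the diagnosis of PTSD assessed pre-treatment and 1-month following the completion of treatment". On method it says: "The primary analysis will use mixed effects regression models". It gives no model terms, covariance structure, missing-data method or auxiliary variables.
- **Withdrawal.** Discontinuation of Subjects (Item 6) opens with "Subjects may be discontinued from study treatment and assessments at any time". Its deterioration criteria include "a 25% increase in the PCL-5 at any time during the study", "Patients with a CGI-I score ≥ 6 at any post-baseline visit" and the onset of active suicidality. Intolerance and investigator judgement are also listed. Risk Minimization adds that a participant whose condition significantly worsens leaves the research protocol and continues usual treatment. No exit or later CAPS-5 is described for these participants.
- **CAPS-5 schedule.** Three places differ. The analysis plan has pre-treatment and 1 month. The Table of Study Procedures has baseline and a shared 1-month/3-month column, with no mark in weeks 1 to 3. The instrument description under Phase I says "at the beginning and end of the intervention for all participants".

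**The concern.** A mixed model gives valid estimates under missing at random only with respect to the data it contains. In a PCL-5 model, the reading that triggers withdrawal is itself an outcome value, so that cause of loss is accounted for. In a model holding only CAPS-5 at baseline and 1 month, it is not. Participants withdrawn after a PCL-5 rise are likely to have had a poor 1-month CAPS-5. If more of them come from the sham arm, the remaining sham participants look better than the arm really did, and the estimated benefit shrinks. At stake is the clinician-rated part of the primary outcome, when the PCL-5 readings that could correct it are already being collected.

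**Working it through.** **1. The plan's own figure.** Step-by-Step Methods (Item 6) randomises 132 to retain 100. Implied loss is 32/132 = 24.2%, and 50/(1 − 0.24) = 65.8, rounded up to 66 per arm, so the inflation is reproduced. The share of loss due to a PCL-5 rise is not stated. The 50 per arm cannot be reproduced, because no alpha, power, effect size or SD is given.

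**2. What a baseline-only participant contributes.** Take a two-visit model with a common baseline mean, unit variances and correlation ρ. With n₁ and n₂ participants observed at 1 month, the variance of the treatment contrast is (1 − ρ²)(1/n₁ + 1/n₂).
- 50 observed per arm: 0.91 × 0.04 = 0.0364 (ρ = 0.3); 0.75 × 0.04 = 0.0300 (ρ = 0.5); 0.51 × 0.04 = 0.0204 (ρ = 0.7).
- 46 and 54 observed, ρ = 0.5: 0.75 × (1/46 + 1/54) = 0.0302.

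The full information matrix gives the same values with and without the 32 baseline-only participants. For diagnosis, Item 5 requires PTSD on CAPS-5 at entry, so the baseline value is constant and again adds nothing. If baseline means are fitted by arm, these participants enter only through those means, which does not remove the selection.

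**3. Bias on the CAPS-5 score.** This is a simulation with about 400,000 per arm; every input is an assumption except the entry minimum of 25 and the 0 to 80 PCL-5 range (20 items scored 0 to 4).
- Baseline PCL-5 has SD 12, kept within 25 to 80. Weekly PCL-5 is baseline plus a linear trend, a personal slope and noise.
- Where there is an effect, active treatment adds 7 points of PCL-5 decline by week 3 and 5 points of CAPS-5 benefit.
- CAPS-5 change has SD 10 and correlation r with the personal PCL-5 slope.
- Withdrawal occurs at the first weekly PCL-5 at or above 1.25 × baseline, and 1-month CAPS-5 is then always missing. There is no other loss.
- CAPS-5-only is regression on arm and baseline CAPS-5 in those observed. The joint estimate uses sequential regressions by arm on baseline CAPS-5 and all PCL-5 readings.

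| Case (baseline PCL-5 mean; slope SD; noise SD; sham decline) | r | Withdrawn, sham / active | Full data | CAPS-5 only | With PCL-5 | Shortfall |
|---|---|---|---|---|---|---|
| No effect (50; 12; 6; 9) | 0.7 | 8.5% / 8.4% | −0.04 | −0.03 | −0.04 | none |
| Few triggered (60; 12; 5; 15) | 0.7 | 1.5% / 0.4% | −5.00 | −4.85 | −5.00 | 3% |
| Middle (50; 12; 6; 9) | 0.4 | 8.5% / 3.2% | −4.98 | −4.66 | −4.98 | 6% |
| Middle (50; 12; 6; 9) | 0.7 | 8.5% / 3.3% | −4.98 | −4.43 | −4.98 | 11% |
| Many triggered (45; 14; 7; 5) | 0.7 | 21.5% / 11.5% | −4.98 | −4.07 | −4.99 | 18% |
| Many triggered (45; 14; 7; 5) | 0.85 | 21.5% / 11.5% | −5.01 | −3.90 | −5.00 | 22% |

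Shortfall is (full data − CAPS-5 only)/full data; for example (4.98 − 4.43)/4.98 = 11%.

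**4. Against sampling error.** With SD 10 and 50 per arm, the standard error is 10 × √(2/50) = 2.0. The shortfalls of 0.15 to 1.11 points are therefore 0.08 to 0.55 standard errors.

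**5. Bias on diagnosis.** Assume 35% of active and 25% of sham lose the diagnosis, no triggered participant does, and 2.9% of active and 6.6% of sham are triggered. The observed rates are 0.35/0.971 = 36.0% and 0.25/0.934 = 26.8%. The difference is 9.3 points instead of 10.0. Its standard error at 50 per arm is √[(0.360 × 0.640 + 0.268 × 0.732)/50] = 9.2 points. The shift grows with withdrawal: at 11.5% and 21.5% the rates are 0.35/0.885 = 39.5% and 0.25/0.785 = 31.8%, a difference of 7.7 points.

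**The case against.** The case on the other side has real force.

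- **The plan is silent, not wrong.** It does not exclude a joint model or imputation, so there is no specified CAPS-5 model that drops anyone. That stands. The point concerns what happens if the analysis is run on CAPS-5 alone, which the text leaves open.
- **CAPS-5 is named for diagnosis, not score.** That also stands. The percentages in the table apply to a continuous score; on diagnosis the shift in the main illustration is under one percentage point, well inside sampling error.
- **The trigger may be rare and need not end assessments.** Discontinuation is worded as permissive, and the reference value for the 25% rise is not stated; baseline is assumed here. The rule is relative: a start of 25 needs a rise of 6.25 points, while a start above 80/1.25 = 64 cannot trigger it. So those triggered are not simply the most severe participants. This limits the size of the bias but leaves the mechanism intact.
- **Another CAPS-5 may exist.** An end-of-intervention or 3-month CAPS-5 appears in parts of the document. It would help only if also obtained from withdrawn participants.
- **The remedy's success is built in.** In the simulation, loss depends only on observed PCL-5, so a joint analysis must recover the truth. Withdrawals for CGI-I, suicidality or intolerance are not covered by PCL-5 alone.

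A reader might infer that the CAPS-5 result is certain to be biased, that the false-positive rate is inflated, or that one narrow percentage describes the error. The documents support none of these. They give no trigger rate, and the bias vanishes in the simulated case with no effect and equal withdrawal.

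**Conclusion.** The concern holds conditionally. It requires that 1-month CAPS-5 is missed after a PCL-5 rise, that PCL-5 and CAPS-5 courses are related, and that triggered withdrawal differs by arm. Hypothesis 1 (Item 4) makes the last likely if the treatment works, and the bias is then toward no effect. If active participants were triggered more often, the selection would flatter iTMS; that case was not simulated.

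The size cannot be fixed from the documents. The assumed inputs give roughly 3% to 22% of a continuous CAPS-5 effect. On diagnosis the shift is 0.7 of a percentage point at 6.6% sham and 2.9% active withdrawal, and more if withdrawal is heavier. These are illustrations, not bounds. The point is a cheap improvement to the analysis, not a flaw that invalidates the trial.

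**What to change.** Before unblinding, prespecify one of two approaches for 1-month CAPS-5, applied to all randomised participants:

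1. Multiple imputation within arm from baseline CAPS-5, every PCL-5 reading including the one that triggered withdrawal, and the collected CGI and suicidality measures. Impute the score, with diagnosis derived from it or imputed alongside, then run the planned analysis.
2. A joint mixed model for CAPS-5 and PCL-5.

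State that either approach assumes data are missing at random given the measures included. The procedures table marks CGI and the suicidality measures at baseline, week 3 and follow-up only, so early withdrawals may lack them unless a value was recorded when the criterion was applied. Say how such cases are treated.

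Reconcile the CAPS-5 time points in the instrument description, the procedures table and the analysis plan, and state whether CAPS-5 is analysed as score, diagnosis or both.

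The cost is wording, modest extra programming and reliance on the modelling assumption. PCL-5 is already scheduled, so no new visit is needed and no clinical rule changes.
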